9.8.3 Statistical Methods

Descriptive analyses

For continuous variables, the following measures will be reported: the number of patients with non-missing data, the number of patients with missing data, mean, standard deviation, median, quartiles, and minimum and maximum. For categorical variables, the number of non-missing observations (number and percentage of total non-missing; n, % of total), as well as the number of patients with missing data will be reported.

Description of analysis sets and characteristics at enrolment

Number and percentage of patients per cohort (cladribine or fingolimod) will be presented by analysis sets as well as by participant country.

The description of demographic characteristics and other characteristics at enrolment for both cohorts will be presented using summary tables to allow a general comparison. Appropriate statistical tests will be applied to compare the cohorts. Further details on methodology will be provided in the SAP.

Assessment and comparison of safety outcomes

Primary analysis

Using the intention-to-treat exposure definition, the crude and adjusted incidence rates of the different AESIs along with 95% CIs will be estimated in both oral cladribine patients and fingolimod patients. The following categories of AESI will be considered: malignancies (excluding NMSC), herpes zoster infections, tuberculosis, PML, other opportunistic infections, and other severe infections.

To compare the incidence of AESI between oral cladribine patients and fingolimod patients adjusting for key prognostic factors (as defined *a priori* in the SAP for each AESI), the incidence rates ratios of the AESI together with the 95% CIs will be estimated by Poisson regression models

adjusted for the key prognostic factors (including prior use of immunomodulatory/immunosuppressive agents) and displayed by means of forest plots.

Sensitivity analyses for the primary analysis

The following sensitivity analyses will be performed for the primary analysis:

- 1) For the analyses regarding malignancies, 2 sensitivity analyses excluding all malignancies occurring within 6 and 12 months after cohort entry will be performed to account for the latency period for malignancies to develop (induction period of 6 and 12 months after treatment initiation).
- 2) Another set of sensitivity analyses will consider an as-treated analysis. To capture the effect of treatment switch, time-dependent exposure variables indicating on-going treatment (oral cladribine (yes/no), fingolimod (yes/no) will be included in the Poisson regression model. At treatment switch, a latent period of 6 months will be applied to the discontinued treatment. Thus, events occurring within 6 months after the switch will still be considered as related to the discontinued treatment. Censoring at 12 months instead of 6 will also be considered for the analysis regarding malignancies.
- 3) Another set of sensitivity analyses will consider an on-treatment analysis in which the ITT exposure definition is used but patient follow-up time will be censored 6 months (or 12 months) after oral cladribine or fingolimod treatment discontinuation.
- 4) Further sensitivity analysis by malignancies grouped will be conducted as follows and described in the SAP: any malignancies including NMSC, solid tumors only, and hematological tumors only.
- 5) Sensitivity analysis will be conducted using the time since last dose received exposure definition described in Section 9.4.1.
- 6) As an alternative to the parametric regression analysis, the cumulative incidence of AESIs during follow-up will be described using a non-parametric approach. Details of the description of the analysis will be given in the SAP.
- 7) A sensitivity analysis where the analyses are adjusted on propensity scores will be performed. The propensity scores (probability to be included in oral cladribine group at start of follow-up) will be calculated conditional on all potential confounders (eg, key prognostic factors and any other variables possibly associated with treatment selection and/or outcomes).

Secondary analyses

Lymphopenia

The incidence rate of severe lymphopenia in oral cladribine patients as well as the 95% CI will be estimated. The adjusted incidence rates and the 95% CI will be estimated separately for the first severe lymphopenia event and for all the severe lymphopenia events using the Poisson regression adjusting for the key prognostic factors. The results will be displayed by means of forest plots.

While patients have ongoing severe lymphopenia, they are not at risk of a new event of severe lymphopenia, therefore time with ongoing severe lymphopenia will be censored from the analysis.

Analysis of duration of severe lymphopenia will be descriptive using Kaplan-Meier curves stratified by key prognostic factors.

Effect of prior use of immunomodulatory/ immunosuppressive agents on the occurrence of AESI

The effect of the prior use of immunomodulatory (IM) agents or immunosuppressive (IS) agents on the incidence of AESI in patients initiating oral cladribine or fingolimod will be assessed by including such variables into the Poisson regression model. A separate variable will be used for prior IM or IS agents used for treatment of other conditions than MS.

Description of sequential use of DMT after cladribine treatment in patients who experience a recurrence of the disease activity

Number and percentage of patients that experience a recurrence of the disease activity in both oral cladribine and fingolimod cohorts as well as type of DMT given after oral cladribine or fingolimod (immunosuppressive or immunomodulatory agents), such as switch to fingolimod, oral cladribine, interferons beta-1a, interferons beta-1b, natalizumab, teriflunomide, glatimater acetate, or other DMTs.

Subgroup analyses for the RRMS population

The primary analysis described above will be performed for the subset of patients with RRMS treated with oral cladribine and in all patients included in the fingolimod cohorts. This analysis will be limited to patients with available information on the clinical course of the disease at enrolment.

Exploratory analyses

Description of discontinuation

Number and percentage of patients discontinuing initial treatment (oral cladribine or fingolimod) will be computed for both cohorts, and presented together with the main reasons for discontinuation. Treatment start and discontinuation dates will be taken into account. Kaplan-Meier curves will be used to characterize time to treatment discontinuation.

Relationship between severe lymphopenia and AESI

Relationship between severe lymphopenia and AESI in the oral cladribine cohort will be further evaluated by looking at the temporal associations of the respective events.

The following 2 variables will be constructed:

- 1) Time since lymphopenia as a continuous variable
- 2) Number of lymphopenia episodes: $0, 1-2, \ge 2$.

AESI will be tabulated (number and percentage) with respect to the above variables.

In addition to quantify the temporal association between severe lymphopenia and AESI, the above variables will be added to the analysis of AESI.

Full details on the methodologies mentioned above will be described in the SAP.

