In addition, other delayed health effects, including the possibility of an increased risk of developing malignancies remains uncertain. As a consequence, the CHMP has requested the Applicant to conduct a study to assess the potential of an increased risk of developing malignancies through a comparative post-authorization safety study (PASS).

Fingolimod has been selected as a comparator given that both fingolimod and cladribine have oral administration and target a similar indication. Therefore, possible indication bias and selection bias are minimized. Similar to oral cladribine, the core pharmacodynamic effect of fingolimod is a dose-dependent reduction of the peripheral lymphocyte count to 20-30% of baseline values. This is due to the reversible sequestration of lymphocytes in lymphoid tissues. Furthermore, fingolimod is widely used, which will facilitate patient recruitment.

This PASS aims to further evaluate the safety profile, including long-term safety aspects, of oral cladribine tablets in patients with highly active MS who are newly initiating this drug under a real-world post-marketing setting, as compared to patients with highly active MS who are newly initiating fingolimod. The study has a focus on measuring the occurrence of adverse events of special interest (AESI), defined as severe infections, herpes zoster infection, tuberculosis, PML, other opportunistic infections, and malignancies.

Therefore, this prospective, observational cohort study will follow-up 8,000 patients in total for an extended period of 10 years, thus allowing the detection of low-frequency and late-onset events

that were detected with difficulty during Phase III clinical development. This PASS is part of the Risk Management Plan (RMP) as an additional pharmacovigilance activity to further characterize the safety profile of oral cladribine in a real-world setting. In addition, data generated through this PASS will be used to measure the effectiveness of some risk minimization measures in line with what is specified in the RMP.

8 Research Question and Objectives

The research questions is:

What is the safety profile in terms of AESI (severe infections, herpes zoster infection, tuberculosis, PML, other opportunistic infections, and malignancies) in patients with highly active MS newly initiating oral cladribine in the routine clinical practice, and how is this profile comparatively to the safety profile of highly active MS patients newly initiating oral fingolimod?

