9.2.4 Study Period

Cohort entry date is defined as the date a patient newly initiates cladribine or fingolimod. The cohort entry date can only be after cladribine has become available in the country participating to the study.

In the data sources using additional primary data collection, patients will be followed from the cohort entry date after they have signed the informed consent until the end of the data collection period (10 years), loss to follow-up, withdrawal of their informed consent or death, whichever comes first. In the data sources with secondary use of data only, patients will be followed from the cohort entry date until the end of the data collection period (10 years), emigration, or death, whichever comes first. The overall study duration is estimated to be of maximum 15 years in both cohorts, based on an estimated recruitment period of 5 years and a follow-up of 10 years for each patient.

Due to the prolonged action of oral cladribine and the potentially long latency period of some of the study outcomes, patients who discontinue the study treatment will still be followed until the end of the 10-year period after enrolment, even if the patients switches to any other DMT.

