Severe lymphopenia: Any occurrence of severe lymphopenia during the study period, classified as Grade ≥ 3 . As per the Common Terminology Criteria for Adverse Events (CTCAE) (V4.03: June 14, 2010) from the National Institutes of Health, the grades of lymphopenia are defined based on laboratory test results that indicate a decrease in number of lymphocytes in a blood sample:

- Grade 3: $<500 200/\text{mm}^3$; $<0.5 0.2 \times 10^9 /\text{L}$
- Grade 4: $<200/\text{mm}^3$: $<0.2 \times 10^9/\text{L}$

Duration of severe lymphopenia: Defined as the interval from the finding of severe lymphopenia until resolution, which is achieving a CTCAE Grade 1 (less than lower limit of normal [LLN] to 0.8×10^9 /L) or normalization (above LLN). Patients may contribute for more than one episode to this analysis if, after resolution as defined, severe lymphopenia occurs. The frequency of lymphocyte counts in patients with severe lymphopenia will be described with special emphasis on the number and timing of lymphocyte counts in relation to oral cladribine dosing.

Treatment interruption: In the oral cladribine cohort, discontinuation will be further defined as stopping the treatment before completion of a treatment course. Discontinuation will be considered temporary if the patient restarts the same or the second treatment course with a delay of up to 6 months. Otherwise, it will be considered permanent. With regards to discontinuation in the fingolimod cohort, it will be considered as temporary discontinuation if the patient restarts fingolimod within 90 days after temporary discontinuation or permanent discontinuation if there are no more records of fingolimod thereafter.

Treatment discontinuation: Treatment discontinuation will be directly recorded by the treating physician and includes any permanent treatment discontinuation (excluding treatment interruption), regardless of the reason for discontinuation. Reasons and dates for discontinuation will also be captured. The treatment stop date will be used to derive the date of treatment discontinuation.

For complete and accurate information, for each of the outcomes defined above, the data collected will include as much detail as possible to corroborate diagnosis, including but not limited, to histopathologic results, and relevant laboratory and imaging results. In addition, the following two outcome categories will be differentiated:

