9.8.2 Derived and Transformed Data

Calculation of person-years of follow-up

Follow-up time for each patient will be calculated from the cohort entry date (initiation of oral cladribine or fingolimod) to the earliest of the following: event of interest, death, end of follow-up, withdrawal of informed consent, emigration or loss to follow-up. For a given non-recurrent event (e.g. first malignancy), the patient follow-up will not be censored for the other events of interest, and the patient will continue to contribute to the risk time for these other events.

Severe lymphopenia duration

Severe lymphopenia duration is defined as the interval from the finding of severe lymphopenia (Grade \geq 3) until the finding of its resolution (Grade 1 or 0). Given that no regular blood tests are requested per protocol, there is a risk to overestimate the duration of lymphopenia. However, in patients with severe lymphopenia, this risk of bias will be reduced because the physician would be expected to perform a closer follow-up with more frequent blood testing.

Handling of missing data

Methods commonly used in non-interventional studies for handling missing data will be applied. Descriptive analyses will be performed using available data. The number of patients with missing data will be reported for each measured variable in the study. In descriptive analyses, missing data will be described separately and not included in the denominator for the calculation of the percentage for each category of a particular variable.

Full details on handling missing data will be described in more detail in the SAP which will describe the methods for identifying where missing data methods should be applied, the techniques for identifying the type of missing information and the appropriate imputation methods to be used, if any, as per European Medicines Agency (EMA) 2011 guidance on missing data.

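### The cladribine lymphopenia incidence and duration analyses have no rule for a later lymphocyte-lowering drug, so episodes driven by a switch (for example to fingolimod) can be counted as cladribine episodes

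*Protocol*

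**What the plan says.** The secondary objective (Protocol Section 8.2) is to characterise the incidence and duration of severe lymphopenia in patients newly initiating cladribine. Section 9.1.2.2 places the outcome at cohort level. The rules that govern the count are spread over several sections:

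- **Outcome (9.4.2):** "Any occurrence of severe lymphopenia during the study period, classified as Grade" 3 or above. It is not tied to the drug being taken.
- **Follow-up (9.2.4):** patients who stop the study drug "will still be followed until the end of the 10-year period after enrolment, even if the patients switches to any other DMT".
- **End of person-time (9.8.2):** the earliest of "event of interest, death, end of follow-up, withdrawal of informed consent, emigration or loss to follow-up". Starting another DMT is not on the list.
- **Analysis (9.8.3):** "The incidence rate of severe lymphopenia in oral cladribine patients as well as the 95% CI will be estimated", for the first event and for all events. Only time with ongoing severe lymphopenia is removed.
- **Duration (9.4.2, 9.8.2):** "Defined as the interval from the finding of severe lymphopenia until resolution", meaning Grade 1 or normal. Nothing stops or splits an episode at a new drug.

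Two further statements matter. The paragraph of 9.8.3 on later DMT lists examples "such as switch to fingolimod, oral cladribine, interferons beta-1a". The Study Rationale in Section 7 says that "the core pharmacodynamic effect of fingolimod is a dose-dependent reduction of the peripheral lymphocyte count to 20-30% of baseline values".

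**The concern.** Taken together, these rules let a patient finish cladribine, start fingolimod years later, fall below the Grade 3 limit because of fingolimod, and be counted as a severe lymphopenia event in the cladribine cohort. While fingolimod continues, the count may stay below the recovery limit, so the recorded duration would partly measure time on the next drug. The exploratory analysis of lymphopenia and AESI in 9.8.3 uses the same episodes.

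The study exists to characterise cladribine's risks, and severe lymphopenia is named in Section 7 as an important identified risk. Readers will take the rate and the duration curve as properties of cladribine. The protocol sees the switching problem elsewhere: 9.4.1 defines an as-treated exposure for exactly this switch. But 9.8.3 lists that analysis only under sensitivity analyses for the primary analysis. Section 9.10 discusses overestimated duration only as a result of sparse blood testing.

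**Working it through.** **1. The plan's nearest figure.** No figure is given for the lymphopenia analysis. Table 3 gives 32,907 person-years at Year 15. With 4,000 patients, ten years each, a full first year and then 5% yearly dropout taken at mid-year:

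4,000 x [1 + 0.975 x (0.95^0 + ... + 0.95^8)] = 4,000 x [1 + 0.975 x 7.395] = 32,841, which is 0.2% from 32,907.

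Other dropout timings give 31,292 to 33,580. The figure is thus consistent with dropout as the only loss and no censoring at a switch. The first four years contribute 4,000 x [1 + 0.975 x 2.8525] = 15,125, so 1 - 15,125/32,841 = 54% of person-time lies beyond year 4.

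**2. Can fingolimod alone meet the outcome?** Limits from 9.4.2: Grade 3 below 0.5 x10^9/L, recovery at 0.8. Effect from Section 7: 20-30% of baseline.

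- Below 0.5 if baseline is under 0.5/0.30 = 1.67 (at 30%) or 0.5/0.20 = 2.5 (at 20%).
- Below 0.8 if baseline is under 0.8/0.30 = 2.67 or 0.8/0.20 = 4.0.
- Assumed baselines of 1.5, 1.8 and 2.0 give 0.30-0.45, 0.36-0.54 and 0.40-0.60. All are under the recovery limit, and all or part of each range is under the Grade 3 limit.

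The 20-30% is a typical effect, not a value for every patient, so this shows that it can happen, not how often.

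**3. Illustration of the first-event rate.** From the protocol: 4,000 patients, 20-25% with Grade 3 or higher lymphopenia on cladribine, about 5% dropout a year. Assumed: those events fall in years 0-2; 5-20% of event-free patients switch to fingolimod at year 3 or year 5; 20-60% of switchers reach Grade 3 or higher within six months.

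- Censored at the switch: 762 (20%) to 953 (25%) first events.
- Not censored: 786 to 1,260 first events, of which 2.4% to 30% are post-switch.

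| Case (switch at year 3, share 20%) | Censored, per 100 PY | Not censored, per 100 PY | Change |
|---|---|---|---|
| Cladribine 25%, post-switch risk 20% | 953/21,367 = 4.46 | 1,055/23,811 = 4.43 | -0.7% |
| Cladribine 20%, post-switch risk 60% | 762/22,555 = 3.38 | 1,089/23,906 = 4.56 | +34.9% |

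These are the extremes of the grid. The rate can fall because post-switch follow-up adds late person-time to the denominator as well as events to the numerator. If the post-switch risk is only 1-10%, the same model gives a change of about -12% to just under 0. For example, with 25%, a 20% share, year 3 and a 1% risk, the uncensored rate is 959/24,363 = 3.94 against 4.46.

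**The case against.** **The cohort-level count is legitimate.** The objective concerns patients initiating cladribine, and the outcome is at cohort level. This stands: the full-follow-up estimate is a valid description of initiators. It does not answer how much lymphopenia cladribine causes, and no main estimate in 9.8.3 does.

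**The abstract already covers it.** The Section 4 Abstract extends time-since-last-dose and on-treatment analyses to the secondary analyses. This is partial. Section 9.8.3 lists them for the primary analysis only. The on-treatment version is triggered by discontinuation, which 9.4.2 defines for cladribine as stopping before a course is completed, so a completer who later starts fingolimod may never be censored. Time since last dose separates late events but does not identify the later drug.

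**Adjustment could handle it.** Section 9.3.3 lists follow-up immunosuppressive therapy, with fingolimod among the agents, as a risk factor, and the lymphopenia rate is adjusted for key prognostic factors left to the SAP. Nothing excludes later fingolimod from those factors, but nothing includes it. The follow-up, outcome and resolution rules are already fixed in the protocol without a switch rule.

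**Recording stops at four years.** Section 11.4 limits recording of AESI other than malignancies, with severe lymphopenia in its list, to 4 years. That covers only sources with additional primary data collection, still admits earlier switches, and sits uneasily with 9.2.5, which makes lymphocyte counts a mandatory outcome variable with collection over the full study period.

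**The effect may be small.** Section 7 reports lymphopenia as a common reaction on fingolimod, the band below 1 in 10. A label frequency is not a laboratory-grade rate, but taken at 1-10% it gives 4,000 x 5-20% x 1-10% = 2 to 80 patients. This stands as a caution about size.

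**Conclusion.** The concern holds as a matter of attribution. As written, the severe-lymphopenia incidence and duration analyses keep counting after a switch to a drug that the protocol itself describes as strongly lymphocyte-lowering, and no main analysis separates those episodes.

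A reader might infer that the headline incidence is therefore inflated, by hundreds of patients, or that post-switch episodes last for years. The documents do not support this. They give no switch share, no post-switch Grade 3 or higher risk and no switch time, and counts come only from routine practice. The -1% to +35% rests wholly on the assumed 5-20% and 20-60%; lower risks push the rate down, so even the direction is open. For duration the mechanism is clearer, because the recovery limit is hard to reach on fingolimod at ordinary assumed baselines, but its extent is also unknown. Nor is the cohort-level estimate an error. It is incomplete when read as a cladribine risk.

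**What to change.** In Section 9.8.3:

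1. Keep the full-follow-up cohort estimate as the description of initiators.
2. Beside it, report incidence and duration with person-time and episodes split or censored at the start of a subsequent lymphocyte-lowering DMT or immunosuppressant, from a list fixed in the SAP. Censoring at the first dose of any DMT would be too broad. It would also conflict with the 6-month carry-over in 9.4.1 and 9.8.3, which still assigns events to the discontinued drug, so apply that convention or show results with and without it.
3. Use this second estimate when lymphopenia is interpreted as a cladribine risk and in the lymphopenia-AESI analysis.
4. Tabulate post-switch episodes by the drug taken.
5. State that the abstract's sensitivity analyses apply to lymphopenia, triggered by the start of the next DMT and not only by cladribine discontinuation.
6. Reconcile the recording windows in 9.2.5 and 11.4.

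The cost is analysis wording, since DMT start dates are already collected (9.3.1). Some late person-time is lost from the second estimate, and censoring at a switch may be informative. The retained full-follow-up estimate lets a reader see how much that matters.

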The types of malignancies reported in the oral cladribine clinical program were in line with what is reported in the general population and in patients with MS. No malignancy pattern reflective of immunosuppression was observed, and no malignancies were seen in cell types most affected by cladribine (eg, lymphomas). There is no evidence of a dose effect of oral cladribine on malignancy occurrence and with cladribine, there was no change in the risk of malignancy over time. The overall malignancy rate with cladribine was similar to the rates observed with other DMTs approved in MS. In summary, there is no conclusive evidence for an increased risk of malignancy with oral cladribine compared to placebo with a risk difference of 0.2033 per 100 PY (95% confidence interval [CI]: -0.0785, 0.3947) in the overall exposed cohort. An independent meta-analysis of study results from Phase III trials of DMTs used in RRMS (Pakpoor, 2015) showed that the malignancy risk profile of cladrbine in the CLARITY study was comparable to that observed in similar trials with other DMTs.

Fingolimod

Fingolimod (Gilenya) is an orally available DMT currently approved in the European Union (EU) and in Australia for the treatment of highly active RRMS in the following patient groups: 1) patients with highly active disease despite a full and adequate course of treatment with at least 1 DMT; or 2) patients with rapidly evolving severe RRMS defined by 2 or more disabling relapses in 1 year, and with 1 or more Gadolinium enhancing lesions on a brain MRI or a significant increase in T2 lesion load as compared to a previous recent MRI (European Medicines Agency, 2011).

Side effects commonly found in patients treated with fingolimod during clinical trials with an observation period of 1 (Cohen et al., 2010), or 2 years (Kappos et al., 2010) include dose-dependent, self-limited bradycardia and atrioventricular conduction block, macular edema, mild arterial hypertension, self-limited liver enzyme elevation and skin cancer. Higher doses of fingolimod (1.25 mg) than the approved 0.5 mg dose were associated with higher frequency of lower respiratory tract infections (Kappos et al., 2010).

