Confounding by indication and/or channeling bias may result from selective prescribing of a specific medication to patients with a different clinical profile (eg, more severe disease). This bias can also arise because of differences in the contraindications and warning and precaution sections between fingolimod and oral cladribine. This will influence drug prescription and, if related to the outcome, act as a confounding factor.

Oral cladribine will be a new drug coming on the market at the start of this study. Thus, patients newly initiating oral cladribine at the very beginning of the study might be different from patients treated with fingolimod or patients who will be treated in later years (eg, with more comorbidities, lack of treatment responsiveness, particular safety profile, not stabilized with other available MS treatments). This effect is often observed when a new drug enters the market and is known as channeling bias. This effect will tend to decrease upon study course.

To address this potential bias:

- Subgroup analysis restricting the study cohorts to patients with RRMS will give insight on any potential impact of indication on the study results.
- Adjustment of outcomes for confounders and effect modifiers will minimize any differences that are due to the presence of different background risk;
- Propensity score adjustment might be used if the 2 cohorts are shown to have statistically significant key differences in characteristics at enrolment.

Limitations related to data sources

Danish data cannot leave Denmark and must be analyzed on the server of a Danish register holder. This limitation can be overcome by running the pooled analyses on the server of a Danish register holder, where a dedicated virtual server space will ensure secure data storage.

In all Nordic countries, the national healthcare registers have a lag time of 3-12 months. Thus, for example data for the anticipated final study year 2033 will be available during 2034. The study period in the Nordic countries is suggested to end 1 year earlier than for the countries using additional primary data collection, to enable holding the suggested timelines. The target study cohort sizes have been defined across all countries and thus the population sizes to be collected per individual country can be adjusted.

Missing variables

- The OFSEP database in France does not collect data on the date of diagnosis, only on the date of onset.

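### The RRMS subgroup restricts only the cladribine cohort although it is relied on as restricting both, and the protocol gives three different rules for the propensity-score analysis

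*Protocol*

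**What the plan says.** **RRMS subgroup.** Under the subgroup heading in Protocol Section 9.8.3, the primary analysis is to be "performed for the subset of patients with RRMS treated with oral cladribine and in all patients included in the fingolimod cohorts". The next sentence adds: "This analysis will be limited to patients with available information on the clinical course of the disease at enrolment". Section 9.10, in its list of measures against confounding by indication and channelling, says: "Subgroup analysis restricting the study cohorts to patients with RRMS will give insight on any potential impact of indication on the study results".

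**Who can be in the fingolimod cohort.** Section 7 describes fingolimod as "currently approved in the European Union (EU) and in Australia for the treatment of highly active RRMS". The inclusion criteria in Section 9.2.2 require initiation under the local MS label and do not require a recorded RRMS course. Section 9.2.3 defines both cohorts with the same R(R)MS term. Clinical course at enrolment is a collected variable for both cohorts (Section 9.3.1).

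**Propensity score.** Item 7 of the sensitivity analyses in Section 9.8.3 says: "A sensitivity analysis where the analyses are adjusted on propensity scores will be performed". That score is to be built on all potential confounders. Section 9.10 says: "Propensity score adjustment might be used if the 2 cohorts are shown to have statistically significant key differences" in enrolment characteristics. The abstract's sentence is grammatically broken. It speaks both of correcting baseline imbalance with the score and of considering that adjustment.

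**The concern.** A subgroup meant to show whether indication drives the result should compare like with like. As Section 9.8.3 stands, disease course filters one cohort and not the other, so any fingolimod patients with another course remain in the denominator of the rate ratio. If their event rates are higher, the ratio is pulled down, which in a safety study means away from detecting harm from cladribine. A reader of Section 9.10 would believe that both cohorts had been filtered.

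The propensity-score wording leaves open whether the analysis is a commitment, an option or a consequence of a test. If the Section 9.10 version were followed, the choice would depend on the data, and on p-values, which say more about cohort size than about the amount of confounding.

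**Working it through.** **1. The plan's own figures.** The protocol gives no figure for the subgroup or for baseline balance. Its nearest figure is Table 4: at Year 15, with 32,907 person-years and a true relative risk of 1.3, the probability of an interval above 1 is 46% (background 0.26 per 100 person-years) or 62% (0.40). Taking the person-years as per cohort, 10,000 Poisson simulations with mid-P 95% intervals give 44.7% and 62.6%. The table reproduces, and neither change below alters it.

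**2. The one-sided restriction.** Let f be the share of fingolimod person-time from non-RRMS patients and k their event rate relative to RRMS patients. With a true ratio of 1 within RRMS, and cladribine restricted to RRMS,

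apparent crude ratio = 1 / (1 − f + f·k).

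The protocol gives neither f nor k, so both are assumptions:

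| f | k = 1.5 | k = 2 |
|---|---|---|
| 0% | 1.00 | 1.00 |
| 5% | 1/1.025 = 0.976 | 1/1.05 = 0.952 |
| 10% | 1/1.05 = 0.952 | 1/1.10 = 0.909 |
| 20% | 1/1.10 = 0.909 | 1/1.20 = 0.833 |

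The direction is also an assumption. With k = 0.67 the ratio moves the other way, to 1.017 at f = 5% and 1.071 at f = 20%. Restricting both cohorts sets f = 0 and returns 1.00 in every case.

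**3. The three propensity-score statements.** Section 9.8.3 item 7 is unconditional and has no significance screen on covariates. Section 9.10 makes use optional and dependent on significant baseline differences. The abstract leaves it for consideration. They cannot all be followed.

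**4. How a significance trigger behaves.** No significance level is stated for the baseline tests; two-sided 0.05 is assumed. The smallest standardised difference that reaches significance with n per cohort is 1.96 × √(2/n). Only 4,000 is a protocol figure (the target per cohort); the other sizes are illustrative.

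| n per cohort | Just-significant difference | Chance that a difference of 0.10 is flagged |
|---|---|---|
| 1,000 | 0.088 | 61% |
| 2,000 | 0.062 | 89% |
| 4,000 | 0.044 | 99% |

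The same imbalance is treated differently according to cohort size. In addition, with 20 independent baseline tests (an assumed number) and no true difference, at least one is significant with probability 1 − 0.95^20 = 64%.

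**The case against.** **The asymmetry may be deliberate.** If fingolimod is labelled for RRMS and entry follows the label, taking all fingolimod patients already means RRMS, and trimming the cladribine cohort aligns it with that comparator. This is a fair reading, and no passage says that any fingolimod label is wider or that patients with progressive disease will enter. It does not close the gap. Section 7 gives the label only for the EU and Australia, while Switzerland and Turkey also take part. Off-label or misclassified patients are possible anywhere. Section 9.2.3 uses the same R(R)MS term for both cohorts. If the reading is right, restricting both cohorts removes almost nobody.

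**A reader might infer that the protections against channelling fail.** The documents do not support that. The primary Poisson models adjust for key prognostic factors fixed in advance, whatever the baseline tests show (Section 9.8.3), and Section 9.10 lists that adjustment as a separate measure. The RRMS subgroup repeats the primary analysis, including its adjustment, so part of any bias from differing disease course may be removed. The ratios above are crude.

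**A reader might also infer that propensity-score adjustment depends on baseline significance tests.** Only Section 9.10 says so; the analysis section commits to it outright. Nor can it be said that adjustment would be dropped in small early cohorts, because Section 9.8.4 holds back comparisons until enough data have accrued.

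**The baseline tests themselves.** Section 9.8.3 plans tests of enrolment characteristics ("Appropriate statistical tests will be applied to compare the cohorts") as description and does not link them there to any propensity-score decision. Removing them would be a matter of preference.

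**Conclusion.** The point holds as two internal contradictions, one in a subgroup analysis and one in a sensitivity analysis. Section 9.8.3 restricts one cohort to RRMS where Section 9.10 relies on both being restricted. The possible distortion of a true crude ratio of 1.00 runs from about 0.98 to 0.83 if 5–20% of fingolimod person-time is non-RRMS at 1.5–2 times the event rate. It is nil if every fingolimod patient has RRMS. These shares and rates are assumptions, so the range illustrates what could happen and is not a forecast.

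On the propensity score, item 7 of Section 9.8.3 is sound, and Section 9.10 and the abstract depart from it. The significance condition is the branch to remove. The primary analysis and the stated power are unaffected.

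**What to change.** - **Section 9.8.3, RRMS subgroup:** restrict both cohorts to patients with RRMS recorded at enrolment, so that it matches Section 9.10. The cost is negligible. As written, the analysis already leaves out patients whose clinical course is unknown, so the only further patients removed are fingolimod patients recorded as having another course.
- **Section 9.10 and the abstract:** state that the propensity-score sensitivity analysis is carried out without condition, as in Section 9.8.3 item 7, and delete the dependence on statistically significant baseline differences. If a balance measure is wanted, standardised differences serve better than p-values; the detail can sit in the SAP.

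Both are wording changes with no effect on data collection, sample size or power.
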